sample based on the early UK experience [2]. It is expected that 80 participants in total (with an expected drop out rate of 15%) enrolled at the Urology Centre at Queen's University site will allow a preliminary assessment of efficacy and safety. The UK early experience study reported that 78% (59 participants of a total of 75 evaluable participants) had no subsequent UTI in the 12 months after the vaccine was administered. One participant reported a treatment related rash while <10% of participants experience mild adverse reactions with only one participant temporarily suspending treatment. We anticipate that based on this experience, 80 participants will be sufficient to determine safety and potential efficacy.

Analysis

Primary outcome: The individual participant will be considered a complete responder if they have no UTI requiring antibiotics reported in the 12 months since initiating therapy. A 50% responder rate of all enrolled participants will be considered a very clinically significant result. Based on the results from the first experience report from the UK (Yang and Foley, 2017) with Uromune® which demonstrated that 78% of the 75 women who completed treatment had no subsequent UTIs in the follow-up period, our convenience sample should be sufficient to power our analysis. The primary efficacy endpoint will be considered to have been achieved if a clinically significant and important level of more than 50% of participants undergoing therapy has no reported UTI in the 12 months after initiation of therapy.

Secondary outcome: The number of UTI in individual participants requiring antibiotics in the 12 months after starting therapy will be compared to the number of UTIs requiring antibiotics before therapy is initiated (number over previous 12 months or 2 X the number over the preceding 6 months). The analysis will include individual participant data comparisons as well as the mean number of UTI before and after initiation of therapy in the entire cohort. Based on the results from the comparison of Uromune® vs antibiotics from Spain (Lorenzo-Gomez MF et al 2012) which demonstrated a mean UTI rate after Uromune® therapy (n=136) of 0.36 (CI0.29-0.44) at 6 months, 0.72 (CI 0.60-0.85) at 9 months, the study should be adequately powered to show a statistically significant difference in our convenience sample of participants enrolled with a history of at least 3 UTI in the preceding 12 months.

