Quality of life and satisfaction questionnaires will also constitute secondary endpoints

The analysis for both efficacy and safety will be an intent to treat analysis of all participants who took at least one dose of the Uromune®. A per protocol efficacy analysis will include all participants who completed the 3 month treatment regime.

Interim Analysis Plan and Stopping Rules

An interim analysis will be carried out when 50% of participants reach the 6month follow up interval. Stopping rules will be based on safety considerations – the study would be stopped if >20% (8 participants) experienced Treatment Emergent Serious Adverse Events (TESAEs). Safety will be monitored continuously for the rest of the study and the study will be stopped if at any time, if >20% of participants experience TESAEs.

Summary Statement: Rationale for this Investigator Initiated Early Experience Real Life Clinical Practice Study

We hope that this study will provide guidance for the use of Uromune® (when or if it is released in Canada) by providing information on the best way to manage recurrent UTI in individual participants using their own clinical data (in this case the number of recurrent UTI). The ultimate goal is to reduce participants' suffering (and therefore improve quality of life), participant time spent dealing with this problem, indirect costs (time off work or other activities), antibiotic use, antibiotic resistance and health care utilization (including costs). We plan to undertake this study with great enthusiasm with limited funding (and "in kind" supply of Uromune® from Red Leaf Medical) because of the huge unmet need for better preventative therapy for our Canadian women with recurrent UTI.

Responsibilities:

Principle Investigator ([name]) Responsibilities – will assume sponsor responsibilities: The PI ([name]) will be responsible for protocol development, diary and CRF development, IRB approvals, informed consent, inclusion/exclusion criteria confirmation, safety monitoring, data analysis, and presentation/publication of results..

Supplier (Red Leaf Medical) Responsibilities: Red Leaf Medical will be committed to providing Uromune® for 80 participants to be enrolled in the trial. The Supplier is not committed to provide funds to the investigator, [name] or provide any further financial support for the trial.

References:

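### The secondary before/after comparison sets a 12-month prior count against an unscaled count after therapy, so, read literally, early leavers' shorter follow-up lowers the mean after therapy

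*Combined protocol and SAP*

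**What the plan says.** The Analysis section defines the secondary outcome in one sentence: "The number of UTI in individual participants requiring antibiotics in the 12 months after starting therapy will be compared to the number of UTIs" before therapy. The prior figure is the "number over previous 12 months or 2 X the number over the preceding 6 months", so it always stands for a full year. The comparison is made woman by woman, "as well as the mean number of UTI before and after initiation of therapy in the entire cohort".

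The closing paragraph of the same section says that efficacy "will be an intent to treat analysis of all participants who took at least one dose of the Uromune", so women who leave after dosing stay in. It adds: "A per protocol efficacy analysis will include all participants who completed the 3 month treatment regime". That second set does not require 12 months of follow-up.

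Under Number of Participants, 80 women are planned "with an expected drop out rate of 15"%. The timing of dropout is not given. The Participant Withdrawal and Early Termination sections provide a final visit with a UTI history, but nothing describes collecting infections that occur after a woman has left.

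**The concern.** The plan recognises that window length matters when it doubles a 6-month prior count. It has no matching step for a short window after therapy. A woman followed for 3 months with one UTI and a woman followed for 12 months with one UTI would each contribute a count of 1, although their rates are 4 and 1 per year.

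On that reading, lost follow-up can only lower the mean after therapy, and this happens even if dropout has nothing to do with infection. The study has no comparator arm in which similar dropout could offset the shortfall. The before/after count is also its only estimate of how far the number of UTIs falls, and the Analysis section expects it to show a statistically significant difference.

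**Working it through.** **Inputs from the protocol.** 80 participants and 15% dropout (Number of Participants); prior count on a 12-month scale, mean count after therapy, and at-least-one-dose set (Analysis); at least 3 UTIs in the prior year, so 3 per year is used as the baseline.

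**The plan's own figure.** The 80 is a convenience sample tied to vaccine supply. No test, alpha, standard deviation or power value is stated for this outcome, so there is no calculation to reproduce. The dropout arithmetic is 80 × 0.85 = 68 completers and 12 leavers.

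**Assumptions.** All 12 leave after dosing, the UTI rate r is constant over the year, dropout is unrelated to UTI, and partial counts enter unscaled. Let f be the mean fraction of the 12 months observed in leavers.

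Mean count after therapy = r × (68 + 12f) / 80. Shortfall = 0.15 × (1 − f).

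| Leavers' follow-up | f | Shortfall | True mean 1.00 shown as | Fall from 3 shown as (true 66.7%) |
|---|---|---|---|---|
| 9 months on average | 0.75 | 3.75% | 0.963 | 67.9% |
| Even over the year | 0.50 | 7.5% | 0.925 | 69.2% |
| All leave at month 3 | 0.25 | 11.25% | 0.888 | 70.4% |
| Limit | 0 | 15% | 0.85 | 71.7% |

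**Smaller true effects.** A true fall from 3 to 1.5 (50.0%) is shown as 53.8% (f = 0.50) or 55.6% (f = 0.25). With no true change, a mean of 3 is shown as 2.775 or 2.66, an apparent fall of 7.5% or 11.25%.

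**Effect on a test.** This was simulated with N = 80, Poisson counts, a paired t-test at two-sided 0.05 and 20,000 runs; the test, alpha and distribution are assumptions. With no true change, rejection in the vaccine's favour rises from the nominal 2.5% to about 12% (even dropout) or 21% (all at month 3). With a true fall from 3 to 1, power is about 100% either way.

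**Some dropout before dosing.** If half of the 12 leave before the first dose (assumption), 74 women are dosed and 6 of them leave early. The shortfall is 6/74 × 0.50 = 4.1% or 6/74 × 0.75 = 6.1%.

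**A rate that changes.** The Analysis section cites mean UTI figures of 0.36 at 6 months and 0.72 at 9 months. If these are cumulative and the later rate continues to month 12 (both assumptions), the 12-month mean is 0.72 + 0.36 = 1.08.
- Even dropout: leavers average (6 × 0.18 + 6 × 0.72) / 12 = 0.45, so the shortfall is 0.15 × (1 − 0.45/1.08) = 8.75%.
- All at month 3: leavers have 0.18, so the shortfall is 0.15 × (1 − 0.18/1.08) = 12.5%.

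**Check of the remedy.** Person-years observed are 68 + 12f, which is 74 for f = 0.50. Under a constant rate, UTIs per person-year recover r exactly: 80 × 2.775 / 74 = 3.0. Under the changing rate above, the person-time rate is still slightly low: 0.9125/0.925 = 0.986 and 0.875/0.8875 = 0.986, about 1.4%.

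**The case against.** The strongest reply is that the plan is silent on how leavers are counted. The outcome is defined over 12 months, so a woman without 12 months could equally be treated as missing, and the bias could then run either way. A reader might therefore infer that the plan prescribes entering partial counts as full-year counts, or that the bias must favour the vaccine. The documents do not say that. What they do support is narrower: the stated count, on the stated at-least-one-dose set, with no rule for incomplete follow-up, gives an understated mean when followed as written. Dropping leavers would depart from that set.

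Two further replies limit the size. The 15% is attached to enrolled participants, and the Participant Withdrawal section allows for withdrawal before the first dose, so part of it may fall outside the analysis set. And the effect is small against a large true fall, in a secondary outcome of an uncontrolled pilot; the raised false-positive rates need no true change at all and a test that the plan does not name. Both replies stand.

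The per-protocol analysis is no answer, since it admits women with little more than 3 months of follow-up.

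**Conclusion.** The point holds as a conditional one. Read literally, the comparison understates the mean after therapy by 7.5% (even dropout) to 11.25% (all at month 3), with a ceiling of 15%. That rests on all 15% leaving after dosing, a constant UTI rate, and dropout unrelated to UTI. It is about 4% to 6% if half of the dropouts leave before the first dose, and somewhat more than 7.5% to 11.25% if the rate rises during the year. If women leave because of infections, the understatement can be larger.

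The documents do not support the stronger inference that the secondary result would be seriously misleading whatever the true effect. A fall from 3 to 1 per year would be shown as about 69% to 70% instead of 66.7%. The distortion matters mainly if the true effect is small or absent. It is worth correcting before analysis because the remedy is cheap.

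**What to change.** In the at-least-one-dose set, make UTIs per woman-year the before/after measure. Report a rate ratio with 95% CI from a model that accounts for pairing within woman, for example Poisson or negative binomial GEE with robust variance, with period as the factor and log of months observed as offset. State how months observed are defined, for example from Day 1 to the last contact at which a UTI history was taken, up to 12 months.

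Enter a woman who has a 6-month history with her actual 6-month count and 6 months, not a doubled count. Show crude mean counts for women with a full 12 months only as a supplement. Add a sensitivity analysis for dropout related to UTI and for a rate that changes over the year, since the offset alone does not fully correct either.

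The cost is revised analysis wording and slightly more analysis work. The offset needs observed time rather than UTI onset dates, and the visit and phone schedule already establishes that time. The reported reduction will probably be slightly less favourable.

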The proposal is for a real life clinical practice study in which female participants with a predefined history of recurrent UTIs in the previous year will be treated with 3 months of oral vaccine with a further 9 months of follow-up. The primary outcome will be no UTI in the 12 months following initiation of the vaccine (definition of a responder). A clinically significant and important outcome will be defined as a responder rate of 50% (50% of participants who had at least 3 UTIs in the previous year reporting no UTIs after therapy initiated.

Study Protocol

Study Participants

Main Inclusion Criteria:

Eligible participants will include women with at least 3 reported UTI episodes requiring antibiotics in the preceding 12 months or at least 2 reported UTI episodes requiring antibiotics in the preceding 6 months. In both cases, at least one of the episodes must be associated with a positive urine culture with a traditional and accepted uropathogen.

Other inclusion Criteria:

- Female participant \geq 18 and \leq 75 years of age at time of screening.
- Can provide written consent and willingness to comply with all aspects of study treatment and study requirements.
- Individuals who have had at least 3 episodes of a UTI in the past 12 months or 2 UTI episodes in the past 6 months. At least one of the UTI episodes must be associated with a positive urine culture with a traditional uropathogen including Escherichia coli, Proteus spp., Staphyloccous sp., Enterococcus sp., Klebsiella sp., or Pseudomonas aeruginosa.
- Post-menopausal for a minimum of 1 year or negative pregnancy test if participant is of child bearing potential and agreement to acceptable contraceptive use from Screening Visit 1 to final follow up visit if

participant is sexually active. Medically acceptable methods of contraception include hormonal contraception (i.e. estrogen, and/or progesterone or preparations that contain a combination of these hormones), non-hormonal intrauterine device or double barrier method (i.e. condom with foam or vaginal spermicidal suppository, or diaphragm with spermicide) or vasectomy of sole sexual partner. Complete abstinence alone can be used as a method of contraception.

• Free of a urinary tract infection at the time of trial inclusion.

Exclusion Criteria

- History of bladder tumours including uterine, cervical, vaginal or urethral cancer.
- Worrisome post-voiding residual (investigator's discretion).
- Infection related to urinary lithiasis.

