
Protocol Deviations

The study is to be conducted as described in the protocol without deviation unless there is a safety concern. The protocol must not be modified for any participant without the prior consent of the Research Ethics Board responsible at the investigative site.

Termination of the Study

If the Investigator discovers conditions during the course of the trial that indicate that the study should be discontinued an appropriate procedure for termination will be instituted.

Reasons for closure of the trial or termination of the study by the Investigator may include the following:

- Successful completion of the study at study site.
- Failure of Investigator to comply with the protocol, GCP guidelines or regulatory requirements
- Safety concerns

Rationale for Study Design

It would be difficult and really impossible to undertake a large multicenter randomized placebo controlled prophylaxis trial with limited funding. The need for evaluation of this type of intervention in Canadian female patients is unquestionable and the general efficacy and safety of Uromune® in Canadian women can be assessed using an open label real life observational study design employing using each participant's history of UTI as their own individual control. We will be able, within the number of participants planned for enrollment (convenience sample based on the number of individual Uromune® doses to be provided by supporting company) to answer our aim: To determine if Uromune therapy provides a clinically acceptable (efficacy and safety) prophylactic option in lieu of continuous and/or interval antibiotic dosing for Canadian women with a history of recurrent UTI.

We do not want to prove that this intervention is better than other interventions (in fact there are no other real non-antibiotic alternatives) but rather reduce the risk of recurrent UTI in women who are suffering from multiple UTIs requiring antibiotics. Each individual participant will be their own control based on the number of UTIs that are documented over the previous 12 months (to be included participants must meet the criteria of 3 documented UTIs requiring antibiotics over the last 12 months or 2 UTIs requiring antibiotics over the previous 6 months).

Number of Participants: Inmunotek, through its Canadian distributor, has offered the principle investigator at no cost, vaccine product (Uromune®) to treat up to 80 participants. The number of participants enrolled will be a convenience

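### The secondary before/after endpoint allows two different 'before' counts with no written rule for choosing, and doubling scores a woman with 2 UTIs in the prior year as 4

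*Combined protocol and SAP*

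**What the plan says.** The secondary outcome in the Analysis section compares two counts of antibiotic-treated UTIs, per woman and as cohort means. The 'after' count is "The number of UTI in individual participants requiring antibiotics in the 12 months after starting therapy". The 'before' count is the "number over previous 12 months or 2 X the number over the preceding 6 months". No condition is attached to the 'or'.

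Two entry routes exist. The Rationale for Study Design gives them as "3 documented UTIs requiring antibiotics over the last 12 months or 2 UTIs requiring antibiotics over the previous 6 months", and the Main Inclusion Criteria word the second as "at least 2 reported UTI episodes requiring antibiotics in the preceding 6 months". The routes overlap.

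The Rationale for Study Design also defines the control: "Each individual participant will be their own control based on the number of UTIs that are documented over the previous 12 months". It names both routes in the same sentence and does not mention doubling. The Screening visit list includes the number of UTIs in the past 12 months and a review of past treatments, for every participant.

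The power sentence for this endpoint says "the study should be adequately powered to show a statistically significant difference in our convenience sample" and describes the sample as "participants enrolled with a history of at least 3 UTI in the preceding 12 months". It gives no test, alpha, power or standard deviation.

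**The concern.** The study has no concurrent control, so the 'before' count is the whole comparator for this endpoint. If its definition is open, two analysts can follow the plan and report different reductions from the same data, and the choice can be made after the data are seen.

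Doubling also misrepresents the group it most naturally fits. For a woman admitted only on the 6-month criterion, it assumes as many UTIs in the earlier half-year as in the recent one, although her eligibility implies that she had none there.

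A second source of apparent improvement is already present. Women are selected for a recently high count, so the later count tends to be lower with no treatment effect. Doubling adds to this in the scenarios below, and the power sentence mentions neither.

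**Working it through.** There is no stated figure to reproduce, because the plan gives no sample-size calculation for this endpoint. The check is on the definition.

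**1. Enumeration (no assumption about rates).** Let a = UTIs in the last 6 months and b = UTIs in the 6 months before that. The 12-month count is a + b and the doubled count is 2a. A woman is eligible if a + b ≥ 3 or a ≥ 2.

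Eligible by the 6-month route only means a ≥ 2 and a + b < 3. The only solution is a = 2, b = 0. Her 12-month count is 2 and her doubled count is 2 × 2 = 4. With 2 UTIs afterwards, the fall is (2 − 2)/2 = 0% on the 12-month count and (4 − 2)/4 = 50% when doubled.

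Women who meet both criteria:

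| a, b | 12-month count | 2 × 6-month count |
|---|---|---|
| 2, 1 | 3 | 4 |
| 3, 0 | 3 | 6 |
| 2, 2 | 4 | 4 |
| 2, 3 | 5 | 4 |

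**2. Effect on the cohort mean.** Each 6-month-only woman scored 4 instead of 2 adds (4 − 2)/n. This is 2/80 = 0.025 at the planned 80 participants. After the expected 15% dropout, 80 × 0.85 = 68, and 2/68 = 0.029. The documents do not give the number of such women. If 4, 8 or 16 of 80 are assumed, the 'before' mean rises by 0.10, 0.20 or 0.40.

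**3. Illustration with no treatment effect (rates assumed).** The 12-month total T follows a gamma-Poisson distribution with mean 2 per year and shape 2. Given T, the last-6-month count B is binomial(T, 0.5). The entry criteria are applied as above. The expected count after entry, given T, is (2 + T)/(2/2 + 1) = (2 + T)/2. By exact summation, 13.0% of eligible women are 6-month-only and 72.1% meet the 6-month criterion. The mean after is (2 + 4.087)/2 = 3.043.

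| Reading of the 'or' | Mean before | Mean after | Apparent fall |
|---|---|---|---|
| 12-month count for all | 4.087 | 3.043 | 25.5% |
| 6-month-only women doubled | 4.348 | 3.043 | 30.0% |
| All with 2 or more in 6 months doubled | 4.911 | 3.043 | 38.0% |

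The second row agrees with step 2: 4.087 + 2 × 0.130 ≈ 4.348.

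At an assumed common Poisson rate of 5 per year (mean after 5.000), the 'before' means are 5.399, 5.446 and 5.972, and the falls are 7.4%, 8.2% and 16.3%.

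**4. How many women have two differing baselines.** In the mean-2 model, if only women with B ≥ 2 may be doubled, 2B differs from T in 60.7% of eligible women (higher in 50.8%, lower in 9.9%). Without that limit the figure is 88.5% (higher in 50.8%, lower in 37.8%). The plan does not state the limit.

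**The case against.** The strongest defence is that the wording mirrors the two entry routes, so the intent is fairly clear: the 12-month number for women admitted on the 12-month criterion, and the doubled number for those admitted on the 6-month criterion. That is the likely reading, but it is not written down. It leaves women who meet both criteria unresolved, and it is the reading that turns 2 into 4.

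A second defence is that doubling annualises a history known for only 6 months. Screening is planned to collect the 12-month number from everyone, so the plan shows no general gap. It does not guarantee a complete 12-month history for every woman, however, and deleting the doubling outright would leave incomplete histories undercounted. This part stands and shapes the fix.

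Third, the effect may be small. If only 6-month-only women are doubled, the apparent fall rises from 25.5% to 30.0% in one scenario and from 7.4% to 8.2% in the other. This also stands for the cohort mean. It does not help the individual comparisons, where 2 recorded as 4 counts in full.

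Finally, this is a secondary endpoint in an open-label pilot that openly uses each woman as her own control. That limits the severity but does not settle the definition.

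**Conclusion.** The point holds. Two 'before' counts are permitted without a written rule, and the doubled one conflicts with the 12-month own-control count in the Rationale for Study Design. The firm part needs no rate assumption: a 6-month-only entrant has 2 UTIs in the year, is scored 4 if doubled, and adds 2/n to the cohort mean. The percentage falls rest on assumed UTI rates, no treatment effect and complete follow-up. They show direction and rough scale only.

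A reader might infer more than the documents support:

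- That 38.0% is the expected spurious fall. It needs an assumed rate and the widest reading of the 'or'.
- That doubling always inflates. A woman with 5 UTIs in 12 months and 2 in the last 6 goes from 5 to 4.
- That doubling explains most of any spurious fall. In the mean-2 illustration selection contributes 4.087 − 3.043 ≈ 1.04, against 0.26 or 0.82 from doubling. At Poisson mean 5 selection contributes 0.40, against 0.05 or 0.57. The order depends on the reading and the rate.
- That the primary result is affected. The responder endpoint does not use the 'before' count.

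This should be fixed before analysis, but it is not a threat to the primary conclusion.

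**What to change.** 1. Define the 'before' count for every participant as the actual number of antibiotic-treated UTIs in the 12 months before therapy, as the Rationale for Study Design already implies.
2. Have the case report form capture that count. The screening item refers to UTIs experienced, without limiting it to those treated with antibiotics.
3. Keep the doubled 6-month value only as a labelled sensitivity analysis, or for a participant whose 12-month history is documented as incomplete, and report how many such participants there are.
4. Correct the description of the sample in the secondary-outcome power sentence so that it names both entry routes. Women admitted with 2 UTIs do not fit it.
5. Report the before/after change with a 95% confidence interval, and state that part of any fall is expected from the entry criteria alone.

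The cost is one definition, one form check and a few sentences, with no new visits or participants. The reported reduction becomes smaller on average in the scenarios run, though individual counts can move either way. The fix removes the added inflation from doubling. It does not remove the fall due to selection.

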Protocol 19-01: Canadian, Single Centre, Pilot, Open Label Study to Evaluate the Efficacy and Safety of the Bacterial Vaccine Uromune® in Treating Recurrent Urinary Tract Infections in Women.

An Investigator Initiated Study

Version 8.0: 20August2019

Principle Investigator

[name] MD FRCSC Professor of Urology, Queen's University at Kingston ON Tier One Canada Research Chair in Urologic Pain and Inflammation

Supplier of Interventional Product:

Red Leaf Medical [name]

Background:

Recurrent urinary tract infections (recUTIs) are a major clinical problem in Canada resulting in over 500,000 visits to physicians annually. Over 50% of women will suffer from a UTI and 20-30% of women who previously experienced a UTI will develop recUTIs (defined as 3 or more UTIs during a 12 month period). Many women are treated with multiple courses of antibiotics while others are managed with long-term low dose antibiotic therapy. This is contributing to not only the ill health of individual patients being treated with antibiotics (disrupting the natural human microbiome) but also to the alarming rise in antibiotic resistance in Canada. There is a large unmet need to develop alternate strategies to prevent UTIs in women in Canada.

Uromune® is a sublingual spray mucosal type vaccine [1, 2], currently in the prelicense phase development stage and is available in a number of countries in Europe, the UK and New Zealand under various patient programs. Spanish studies comparing Uromune® therapy with antibiotic therapy in women with recUTIs have reported a significant decrease in UTI recurrence with a 90.3% absolute risk reduction (95% CI: 87.2-93.4). There were no reported side effects in any participant in the Uromune arm of the study [3]. An early experience study of women with recUTI in the UK reported that 78% (59/75) had no subsequent UTI in the 12 months after the vaccine was administered. Only one participant reported a skin rash requiring treatment cessation [4].

Rationale:

The proposed study will be undertaken to provide early clinical experience in regard to the efficacy and safety of the vaccine Uromune® in Canadian women identified with recUTI.

Objective:

To determine the effectiveness and safety of Uromune® in preventing recUTI in Canadian women.

Study Synopsis

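### The before/after comparison uses the entry-qualifying UTI count as its baseline, so a significant fall can occur with an inert vaccine and is not by itself evidence of efficacy

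*Combined protocol and SAP*

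**What the plan says.** The stated objective is "To determine the effectiveness and safety of Uromune® in preventing recUTI in Canadian women". Main Inclusion Criteria give two routes of entry. The 12-month route admits "women with at least 3 reported UTI episodes requiring antibiotics in the preceding 12 months". The 6-month route instead requires "at least 2 reported UTI episodes requiring antibiotics in the preceding 6 months".

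The Secondary outcome paragraph of the Analysis section compares each woman's UTIs requiring antibiotics in the 12 months after starting therapy with her count before it, taken as "number over previous 12 months or 2 X the number over the preceding 6 months". Individual comparisons and cohort means are both planned. No test, significance level or standard deviation is named. The paragraph then states that "the study should be adequately powered to show a statistically significant difference in our convenience sample of participants enrolled". It describes those participants as women "with a history of at least 3 UTI in the preceding 12 months".

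Rationale for Study Design says that efficacy and safety "can be assessed using an open label real life observational study design employing using each participant's history of UTI as their own individual control", and that "Each individual participant will be their own control based on the number of UTIs that are documented over the previous 12 months".

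The Exclusion Criteria list current prophylactic antibiotics and add that these must be stopped on the day of screening. The Screening visit already records the number of UTIs in the past 12 months and concomitant medications.

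**The concern.** Women are enrolled because their recent count is high, and that count is then the comparator. Part of a high count is chance. When entry depends on it, the next year's count tends to be lower even if nothing has changed. With no control group, no separate baseline period and no mention of regression to the mean, a test of no change is not a test of no vaccine effect.

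The 6-month rule raises the baseline further for some women. The paragraph also does not say which count applies to a woman who meets both entry criteria.

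At stake is how the result is read. The plan says that each woman's history lets efficacy be assessed, and it expects a significant difference, so a small p-value could be reported as a vaccine effect that it does not establish.

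**Working it through.** **1. Doubling, from the documents alone.** A woman who enters only by the 6-month route has at least 2 UTIs in 6 months and fewer than 3 in 12, so exactly 2 in 12 months. Her baseline is 2 x 2 = 4. With 2 UTIs in follow-up she is scored as (4 - 2)/4 = 50% lower, although her yearly count has not changed. She also lacks the history of at least 3 in 12 months that the power sentence assumes.

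**2. The power sentence.** The plan gives no power figure to reproduce. It cites a mean of 0.36 at 6 months and 0.72 at 9 months. Scaled to 12 months this is 0.72 x 12/9 = 0.96, or 0.72 + 0.36 = 1.08 if the last 3-month increment repeats. For a fall from 3 to 0.96 the difference is 2.04. With 68 completers (80 x 0.85) and an assumed SD of change of 4, power = Φ(2.04/(4/√68) - 1.96) = Φ(2.25), about 99%. For SDs of 1 to 4, either 12-month figure and n = 68 or 80, power is at least 97%. The sentence is plausible, but it describes power to detect any change, including change caused by selection.

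**3. Inert-vaccine simulation.** All inputs other than the entry rule, the baseline rule and n are assumptions.
- Yearly rate λ: gamma with mean m and shape 1/k, k = 0.5 to 2, the same before and after.
- Half-year counts H1, H2: Poisson(λ/2). Follow-up count: Poisson(λ). T = H1 + H2.
- Entry if T ≥ 3 or H2 ≥ 2. Baseline = T if T ≥ 3, otherwise 2 x H2.
- Two-sided 5% paired t-test, counting only significant falls (nominal 2.5%). No prophylaxis withdrawal.

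Share of trials with a significant fall:

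| Pool mean per year | Mean fall | Plan's baseline, n=80 | Plan's baseline, n=68 | Actual 12-month count, n=80 | 2 x 6-month for all who meet that criterion, n=80 |
|---|---|---|---|---|---|
| 1.4-2.3 | 13-41% | 63-100% | 56-100% | 46-100% | 84-100% |
| 3 | 10-18% | 43-84% | 38-79% | 32-69% | 66-98% |
| 5 | 5-8% | 19-31% | 16-27% | 14-23% | 31-59% |
| 8 | about 3% | 9-12% | 9-10% | 8-9% | 17-19% |

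One cell in detail (m = 3, k = 0.5): the mean is 5.08 before and 4.15 after, a fall of 0.93/5.08 = 18%. With actual 12-month counts the baseline is 4.91, so selection accounts for 0.76 of the 0.93. Doubling accounts for the other 0.17, which matches 8.3% of entrants x 2 extra UTIs.

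**4. Cause.** With a baseline year not used for entry (m = 2, k = 0.5), the means were 3.04 before and 3.04 after, and two-sided rejection was 4.9%. The excess comes from using the entry count as the baseline.

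**5. Opposing effect.** A woman on prophylaxis before screening has a suppressed baseline and an unsuppressed follow-up. If 20-40% of the pool were on prophylaxis that halved the rate (assumed), significant falls dropped to about 0.6-61% at a pool mean of 3 and 0-5% at 5.

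**6. Responder rule.** With constant rates and a pool mean of 1 or more, at most 23% of women were UTI-free with an inert vaccine. Redrawing half the women's follow-up rates from the pool gave 15-35% at means of 1-3. Redrawing all of them, an extreme case, reached 58%.

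**The case against.** The strongest reply is that the plan contains an opposing bias. Stopping prophylaxis at screening can raise follow-up counts, and at higher source rates this offsets the selection effect or outweighs it. This stands. It rests on an assumed prevalence and effect, as the source rates do. It also depends on how the exclusion bullet is applied: if women on prophylaxis are kept out altogether rather than entered after stopping, they contribute no such offset.

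Second, no document gives a source rate or spread, so the percentages are scenarios. This also stands. Only the 2-scored-as-4 example needs no model.

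Third, the own-control sentence in Rationale for Study Design goes on to name the 6-month route, so the doubling can be read as annualisation and not as a contradiction. That is fair, and doubling is the smaller contributor. But annualising a half-year chosen because it was high still overstates the year, and the actual yearly count is available.

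Fourth, this is a secondary outcome of a declared pilot. Only the primary outcome has a success rule, and stopping is based on safety. That limits the consequence. The missing control is disclosed, but the selection effect is not.

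A reader might go further and infer that an inert vaccine would usually give a significant fall, or that the false-positive rate always exceeds nominal. The documents do not support either, because the net direction depends on unknown rates and prophylaxis use.

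**Conclusion.** The point holds as a limit on interpretation. A significant before/after fall can arise with an inert vaccine and is not by itself evidence of efficacy. The scored fall of 50% with no change, for women entering only by the 6-month route, follows from the plan's own rules.

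The wider size is conditional. With constant gamma-Poisson rates, n = 80 and no prophylaxis withdrawal, false significant falls ranged from 9-12% at a pool mean of 8 to 63-100% at 1.4-2.3. With prophylaxis withdrawal the net bias may be upward, absent or reversed.

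A reader might also infer either that the responder rule of more than 50% is undermined or that it is untouched. Neither is shown. It is probably robust, given at most 23% UTI-free under constant rates, but rates that vary over time could raise that share.

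The paragraph should be changed. The point does not bear on whether the study can proceed.

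**What to change.** In the Secondary outcome paragraph:

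1. Use each woman's actual 12-month count as the baseline for everyone, and show the 2 x 6-month figure only as a supplementary tabulation. This also settles which count applies when both criteria are met. It lessens the selection effect but does not remove it (32-69% instead of 43-84% at a pool mean of 3), so item 3 is still needed.
2. Qualify the power sentence as referring to any before/after change, not to a vaccine effect. Remove or correct the history of at least 3 UTIs in 12 months for women entering by the 6-month route.
3. State that the change is descriptive, and that a significant fall, or a confidence interval excluding no change, is not by itself evidence of vaccine effect because women are selected on a high baseline count. Replacing the p-value with an interval would not be enough, since both carry the same bias.
4. Report the change separately for women who were and were not on prophylaxis at screening.

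Optional: where records allow, compare follow-up with UTIs in months -24 to -13, a period not used for entry. This adds a screening field, older records may be incomplete, and it assumes stable rates.

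Items 1 and 4 use the UTI history and concomitant medications already collected at screening; items 2 and 3 are wording. Treatment, visits, sample size and the primary outcome do not change. The downside is a less favourable efficacy statement and a smaller apparent fall.
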